SMART Stimulation: Precision Neuromodulation of Cognition in Older Adults
NCT05377411
Document Date: 9/19/2023

Protocol # 202100953

1. Project Title

SMART Stimulation Study: Precision Neuromodulation of Cognition in Older Adults

2. Investigator(s):

[name]
[name]
[name]
[name]
[name]

Staff

[name] M.Sc.: Study Coordinator
[name], B.S.
[name], B.S.
[name], M.S.
[name], B.S.
[name], M.S.
[name], M.S.
[name], M.S.
[name], B.S.
[name], B.S.

3. Abstract:

The current study will investigate methods for enhancing cognitive training (CT) effects in healthy older adults by employing a combination of interventions facilitating neural plasticity and optimizing readiness for learning. Adults over the age of 65 represent the fastest growing group in the US population. As such, age-related cognitive decline represents a major concern for public health. Recent research suggests that cognitive training in older adults can improve cognitive performance, with effects lasting up to 10 years. However, these effects are typically limited to the tasks trained, with little transfer to other cognitive abilities or everyday skills. A pilot randomized clinical trial will examine the individual and combined impact of pairing cognitive training with transcranial direct current stimulation (tDCS). tDCS is a method of non-invasive brain stimulation that directly stimulates brain regions involved in active cognitive function and enhances neural plasticity when paired with a training task. We will compare changes in cognitive and brain function resulting from CT combined with active tDCS versus CT combined with sham tDCS using a comprehensive neurocognitive, clinical, and multimodal neuroimaging assessment of brain structure, function, and metabolic state. A precision dosing algorithm will be used to determine the appropriate levels of current and location of electrodes to deliver current using tDCS. Functional magnetic resonance imaging (fMRI) will be used to assess brain response during working memory, attention, and memory encoding; the active cognitive abilities trained by CT. Proton magnetic

resonance spectroscopy (MRS) will assess cerebral metabolites, including GABA concentrations sensitive to neural plasticity.

We hypothesize that:

- 1) tDCS will enhance neurocognitive function, brain function, and functional outcomes from CT, with combined CT and tDCS providing the most benefit;

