4.3.5. Brain stimulation to potentiate training. Since the pioneering work of Penfield, it has been recognized that sensory, motor and cognitive functions could be altered via electrical stimulation of specific brain regions. In laboratory animals, brain stimulation represented an alternative approach to experimental lesions, enabling both the potentiation and inhibition of neural activity depending on where in the brain stimulation was applied. Until recently, most human brain stimulation studies involved neurosurgically implanted electrodes, which has obvious limitations for general clinical use. **Transcranial direct current stimulation (tDCS)** is a non-invasive brain stimulation method that alters the sub threshold membrane potential of neurons, facilitates neural plasticity and learning, and increases regional blood flow while modulating local GABA concentrations during stimulation.⁶⁹⁻⁸⁹ During tDCS, a weak electrical current is applied to the scalp that penetrates skin, bone, CSF and the meninges to stimulate underlying cortical and subcortical tissue.⁹⁰⁻⁹⁵ tDCS applied to dysfunctional cortical regions improves performance on a variety of cognitive tasks.⁹⁶⁻⁹⁹ Bilateral tDCS to the frontal cortices improves decision-making, attention and working memory performance in older adults.¹⁰⁰⁻¹⁰³ Improvements from a single session of tDCS have been shown to last for up to five years in healthy adults.¹⁰⁴⁻¹⁰⁸ Small pilot RCTs (n=20/group) pairing CT with bilateral frontal tDCS show significant and lasting improvement in older adults experiencing declining cognitive function.¹⁰⁸⁻¹¹² Maintenance of these tDCS and CT effects have been shown to last beyond one year.^{104,105,107,108,110} These studies demonstrate that CT combined with tDCS leads to lasting improvement in CT effectiveness for older adults and patients. Research suggests that increased regional blood flow and decreased GABA concentrations during tDCS facilitate the brain's neural plastic response to paired training tasks.^{75,80,83,84,89,113-117} Pairing CT with tDCS to combat age-related cognitive decline holds great promise for older adults.

To date, all prior trials of tDCS have applied a fixed application strategy (e.g., 2mA for 20 min with electrodes at F3/F4 following the 10-20 EEG system) to target a specific brain region (e.g., the dorsolateral prefrontal cortex) in all tDCS recipients.

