A randomized clinical trial will enroll 40 participants. Cognitively healthy elderly adults, age 65-89 will undergo either a CT intervention in combination with optimized transcranial direct current brain stimulation (tDCS) or sham tDCS control. The CT intervention will employ a suite of adaptive training tasks from the POSIT Science Brain HQ²⁸¹; a well validated CT method for enhancing cognitive functioning in the elderly. Participants will receive tDCS or sham/placebo precision stimulation administered during training.

Participants will be assessed at baseline and after CT (2 weeks). At each time point, a comprehensive neurocognitive, clinical and multimodal neuroimaging assessment of brain function, metabolic state, and brain structure will be conducted.

FMRI will be used to assess brain response during working memory, attention and memory encoding. Proton magnetic resonance spectroscopy (MRS) will assess cerebral metabolites, including gamma-aminobutyric acid (GABA) concentrations, sensitive to neural plasticity in task-associated brain regions.

The central hypothesis of this proposal is that optimized tDCS will increase neural plasticity in task associated brain regions, facilitating effectiveness of CT and transfer to everyday function.

Aim 1. Determine whether neurocognitive improvement and longer-term functional outcome (as measured by “ecological assessment”) are better when CT is coupled with tDCS, an intervention that will increase neural plasticity and augment training effects.

H1.1. Active tDCS combined with CT will amplify effects of CT on measures of attention, working memory, executive functioning, and learning efficiency, while sham tDCS will not.

H1.2. Active tDCS will enhance near and far transfer of CT, but sham will not evidence near or far transfer.

Aim 2. Determine whether CT combined with tDCS leads to greater functional and metabolic brain changes (fMRI, MRS). Effects will parallel Aim 1.

H2.1. Combined CT + tDCS will potentiate decrease activation in working memory and attentional (dorsolateral prefrontal cortex, medial frontal cortex, inferior parietal lobe, supplementary motor association cortex) brain systems, reflecting increased neural efficiency, while CT + sham tDCS will not.

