H2.2 Cerebral metabolite alterations will occur secondary to CT and tDCS, with long-term increase in GABA and *N*-acetyl aspartate (NAA) concentrations, and decreased choline (Cho) and myoinositol (MI) concentrations in the frontal cortex. CT and tDCS will modulate MRS GABA in frontal areas. These effects will be specific to CT.

Aim 3. Investigate the performance of optimized tDCS compared to conventional application within the literature

H3.1. Optimized tDCS + CT will generate augmented behavioral gains beyond those observed under conventional tDCS application.

H3.2 Optimized tDCS + CT will also demonstrate greater physiological changes of functional connectivity within the working memory network and glutamate/glutamine concentrations within the prefrontal cortex compared to conventional tDCS application.

6. Research Plan:

6.1. Experimental design. This study employs a randomized trial design with 40 participants. One factor with two levels [Factor 1 = stimulation type (active or sham) yields two cells. Thus, participants will be assigned to one of two conditions:

- 1: Active tDCS + CT
- 2: Sham tDCS + CT

CT has previously been established with strong effects on cognitive and functional outcomes. Some small clinical trials showed small to large effects of tDCS in conjunction with CT.

Participants will be assessed at two primary time points during the study, plus one screening visit on the front end to be sure they meet all inclusion criteria for the study:

- 1) Informed Consent and Screening Visit
- 2) Assessment Visit #1- baseline pre-training
- 3) Assessment Visit #2- post-2 weeks

This design will enable longitudinal analyses of CT and tDCS effects. We will examine their effects on cognitive performance, functional and metabolic neuroimaging measures, and everyday functional abilities. At each assessment, we will obtain clinical and medical history, neurocognitive measures, and neuroimaging (structural MRI, fMRI, MRS). All participants will undergo neuroimaging at baseline and following training.

Screening	✓	✓	✓	✓		✓		
Assessment Visits Activity Summary	Informed Consent Form	Medical History	Hearing and Vision Tests	Memory and Thinking Tasks	Physical and Medical Self Reports	MRI Screen-Form	NIH tool box	MRI Brain Scan Appt.
Visit #1 Baseline				✓	✓	✓	✓	✓
Visit #2 After 2 weeks (10 days) of Training				✓	✓	✓	✓	✓
Daily Lab Visits	Brain Training Games	Brain Stimulation/Sham	tDCS Sensation Questions					
Days 1-10	✓	✓	✓					

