Protection against risks associated with neurocognitive tests. The neurocognitive assessments have minimal risk associated with them. Some participants experience stress associated with being tested, though this tends to be quite limited. Breaks will be given in those cases. Research staff that collect data have been trained in the conduct of all cognitive function tests by other senior staff members. Research staff members will be certified in the conduct of the cognitive function tests before they work with study participants.

Data and Safety Monitoring Plan:

A data and safety monitoring plan (DSMP) will be implemented to ensure the safety of all participants involved in the study and to ensure the validity and integrity of the data. The PI will be responsible for coordinating activities of the DSMP, including: arranging meetings and communications, and identifying and reviewing relevant participant materials. The data and safety information obtained on each study participant will be reviewed at weekly meetings. The primary goal of the DSMP will be to monitor the progress of the study and safety of participants and if necessary, recommend modifying the study or terminating the study as appropriate.

Concerns that might dictate modification or termination of the study include:

- Participant safety
- Outcome data
- Data quality
- Integrity
- Intervention efficacy
- Recruitment
- Performance

Both the PI and the study staff will review the study weekly and examine reports of adverse incidents and reports of study participant recruitment and follow-up. Throughout the course of the study, information regarding issues deemed critical to the study or to the safety of research participants will be provided to the PI and primary mentors. As a result of receiving this critical information, a meeting to discuss this information may be convened. Information deemed critical would include:

- Serious and non-serious adverse events that may occur
- Suspicion of scientific fraud or misconduct
- Any other issues which may warrant protocol changes or modifications.

Because this is an exploratory study with minimal risk associated with the proposed intervention and limited financial resources, there will not be an external data safety and monitoring board for this study. The research team, however, will follow the procedures for data safety and monitoring as required by the Institutional Review Board at the University of Florida (UF IRB).

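### Aim 3 predicts that optimized tDCS beats conventional tDCS, but the trial randomises only optimized tDCS against sham, so Aim 3 should be restated as exploratory, descriptive benchmarking

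*Combined protocol and SAP*

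**What the plan says.** Section 5 of the combined protocol and SAP sets Aim 3 as "Investigate the performance of optimized tDCS compared to conventional application within the literature". Two directional hypotheses follow.

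- H3.1: "Optimized tDCS + CT will generate augmented behavioral gains beyond those observed under conventional tDCS application".
- H3.2 predicts "greater physiological changes of functional connectivity within the working memory network and glutamate/glutamine concentrations within the prefrontal cortex compared to conventional tDCS application".

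The design has two arms. According to section 5, participants "will undergo either a CT intervention in combination with optimized transcranial direct current brain stimulation (tDCS) or sham tDCS control". Section 6.1 confirms that "participants will be assigned to one of two conditions", active or sham, both with CT. Section 6.5 makes clear that active stimulation is the individually optimized kind. Section 4.3.5 describes conventional tDCS as a fixed application strategy, and no participant here is assigned to it.

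For Aim 3 the document names no benchmark study or value, outcome measure, method of comparison or success rule. It has no statistical analysis section for any aim.

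On status, the abstract says "A pilot randomized clinical trial will examine the individual and combined impact". The Data and Safety Monitoring Plan begins a sentence with "Because this is an exploratory study with minimal risk associated with the proposed intervention", but does so to explain why there is no external monitoring board. Aim 3 and its hypotheses do not carry the exploratory label.

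**The concern.** The randomised contrast answers one question: what optimized tDCS adds to CT compared with sham. It carries no information on conventional tDCS. A conclusion about optimized versus conventional stimulation therefore has to be drawn across studies, and the plan does not say how.

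The simplest route is to compare the gain in this trial's active arm with a gain reported elsewhere. That gain contains the CT effect, the practice effect and the stimulation effect together. The plan expects the CT part to be large: section 4.3.3 says effect sizes generally exceed d = 1.0 immediately after CT, and section 6.2.1 expects CT alone to produce improvement. The sample is also selected, with working memory limited to the 0-75th percentile and people whose modelled dose exceeds 4.0 mA excluded (section 7). Participants train on one of two task sets (section 6.4). Any of these can differ from another study.

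The risk runs both ways. A difference in CT, practice or population could be credited to dose optimisation, or could hide a real benefit of it. Section 8 presents the data as a foundation for larger studies, so a wrong reading would be carried forward.

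**Working it through.** **What the plan lets us reproduce.** Aim 3 has no figure to reproduce. The total of 40 is given without alpha, power, effect size or SD.

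**Hypotheses against design.**

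| Comparison | Randomised here? |
|---|---|
| Optimized tDCS + CT versus sham tDCS + CT | Yes |
| Optimized versus conventional tDCS (H3.1, H3.2) | No; no arm receives conventional tDCS |

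**What each cross-study comparison estimates.** Let c be the combined CT, practice and population contribution to the gain in this trial, and c' the same quantity in a literature trial. Let e(opt) and e(conv) be the effects of stimulation over sham.

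- Active arm against active arm: (c + e(opt)) − (c' + e(conv)) = [e(opt) − e(conv)] + (c − c'). The bias is c − c'.
- Sham-anchored: [(c + e(opt)) − c] − [(c' + e(conv)) − c'] = e(opt) − e(conv). The shared part cancels in each trial, provided the stimulation effect does not itself vary with population or training.

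**Illustrative inputs.** The 40 participants come from section 6.1. The allocation ratio is not stated, so 20 per arm is an assumption. A literature trial of 20 per group is used because section 4.3.5 mentions that size: "Small pilot RCTs (n=20/group) pairing CT with bilateral frontal tDCS show significant and lasting improvement in older adults experiencing declining cognitive function". Also assumed, and not in the documents: gain SD = 1, two-sided 5%, no baseline adjustment, no dropout, and a bias c − c' of 0.3 SD in either direction.

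**Active-arm comparison** (noncentral t, probability of significance in favour of optimized tDCS):

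- Against a 20-person literature arm: SE = √(1/20 + 1/20) = 0.316, df 38, critical t 2.02. With bias +0.3 the noncentrality is 0.3/0.316 = 0.95.
- Against a literature mean treated as error-free: SE = √(1/20) = 0.224, df 19, critical t 2.09. With bias +0.3 the noncentrality is 0.3/0.224 = 1.34.

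| True advantage | Bias | Versus 20-person arm | Versus fixed mean |
|---|---|---|---|
| 0 | 0 | 2.5% | 2.5% |
| 0 | +0.3 | 15% | 25% |
| 0 | −0.3 | 0.2% | 0.06% |
| 0.5 | 0 | 34% | 56% |
| 0.5 | −0.3 (net 0.2) | 9% | 13% |

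**Precision.**

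- Active arm against a 20-person arm: 95% half-width 1.96 × 0.316 = 0.62 SD.
- Sham-anchored, one trial of 20 per group: SE = √(2/20 + 2/20) = 0.447; half-width 1.96 × 0.447 = 0.88 SD. The difference detectable with 80% power is (1.96 + 0.84) × 0.447 = 1.25 SD.

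Anchoring removes the shared bias and costs precision. Baseline adjustment would narrow these intervals by an amount that depends on a correlation the documents do not give.

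**The case against.** The strongest defence is that little is being claimed. The Aim 3 heading begins with *investigate* and discloses a literature comparator. The trial is called a pilot and exploratory, no test or success rule is attached to Aim 3, and neither the abstract's hypotheses nor the central hypothesis in section 5 asserts superiority over conventional tDCS. This limits the harm. It does not remove the mismatch, because H3.1 and H3.2 remain directional and the exploratory label sits elsewhere, for another purpose.

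Three stronger readings are tempting, and the documents do not support them.

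- A reader might infer that H3.1 commits the trial to comparing active-arm gains across studies. The word *gains* does not force that. Section 6.2.1 uses it for gains from stimulation, the abstract for gains associated with CT. The bias argument applies only if the first, unanchored route is taken.
- A reader might infer that nothing about conventional tDCS can ever be said. That is exact only for a randomised comparison. A sham-anchored indirect comparison is possible in principle, though imprecise and dependent on similarity between trials.
- A reader might take the small pilot trials cited in section 4.3.5 as the comparator and object to their populations. Nothing designates them as such, and the papers cannot be judged from their titles.

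It is also fair to say that one sentence barring a superiority conclusion would cure the core defect. The fuller remedy is needed only if a benchmark is to be reported.

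**Conclusion.** The point holds as a mismatch between hypothesis and design. H3.1 and H3.2 predict superiority over a treatment that no participant is assigned, so this trial cannot give randomised support for that conclusion. The optimized-versus-sham comparison behind Aims 1 and 2 is unaffected.

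The size of the problem cannot be known from the documents, which give no literature effects and no analysis for Aim 3. The percentages and interval widths above show scale only and rest on the assumed 20 per arm, gain SD of 1 and 0.3 SD bias. They show that a modest context difference could distort an active-arm comparison in either direction, and that the less biased, sham-anchored alternative is too imprecise to carry a superiority claim. The change should be made. Confidence is high on the mismatch and lower on how the sponsor would have assessed H3.1.

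**What to change.** Restate Aim 3, H3.1 and H3.2 as exploratory and descriptive. Suggested text:

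*Aim 3 (exploratory benchmarking). We will report the baseline-adjusted active-minus-sham standardised effect of optimized tDCS + CT with its 95% CI, beside active-minus-sham effects from sham-controlled trials of conventional (fixed-application) tDCS + CT. Those trials will be selected by a rule on population, CT and outcome domain fixed before unblinding. Active-arm gains will not be compared across studies, and no superiority conclusion over conventional tDCS will be drawn. Where no eligible trial reports an H3.2 measure, we will report only this trial's active-minus-sham effect and state that no comparison with conventional tDCS was possible.*

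State which SD (outcome or change) standardises the effects, and use the same one throughout. Record as a limitation that anchoring does not remove bias if the stimulation effect itself varies with population or training.

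The cost is rewording and a short literature search completed before unblinding, with no new arm, participants or procedures. The downside is a weaker Aim 3 claim. H3.2 may end without an external benchmark, since section 4.2 says these imaging methods have been little used in studies of how CT works.

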1. Hawk Eye- works on visual precision, which helps the brain perceive what you see quickly and accurately so that you can recall it better.
2. Divided Attention- requires the brain to focus in on and react to particular details—matching colors, shapes, and/or fill patterns—while at the same time dismissing competing information.
3. Target Tracker- is designed to help build divided attention by requiring you to track several items moving around your screen at the same time
4. Double Decision- requires visual search and selective attention to peripheral objects among distractors.²⁰ Difficulty gradually increases relative to object similarity, presentation rate, and distractor complexity and eccentricity.

Working Memory

1. To Do List Training- the brain hears a set of instructions, then uses its memory of those instructions to follow them in order. The instructions get longer and more complex over time at the task, making greater demands of your working memory systems.
2. Memory Grid - Auditory processing is one of the most important building blocks of memory. Only when you take in information with crystal clarity can the brain store it accurately and recall it clearly later. In Memory Grid, the task is to match cards representing syllables together.
3. Auditory Aces- Participant will be presented with auditory information about playing cards. The information is presented one card at a time. The task is to decide if the current card information matches the card information presented a specific number of steps back in the sequence.
4. Card Shark- N-back working memory task that varies on whether the current target matches stimuli presented 0-n steps before and presentation speed, leading to increased difficulty,^{44,45} and age-sensitivity⁴⁶.

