6.2. Study participants and randomization procedure. We will recruit 40 older adults (age: 65-89 years). Study participants will consist of healthy individuals who have expressed an interest in taking part in an intervention aimed at optimizing and possibly preserving cognitive functioning and brain health. We will use web-based permuted block randomization to randomly divide participants into the two groups. People with pre-existing dementia, neurological brain disease, or meet criteria for a diagnosis of mild cognitive impairment (MCI) will be excluded, though people with subjective concerns about their cognitive functioning, who do not meet these criteria, may participate. Detailed inclusion/exclusion criteria can be found in Section 7.

6.2.1. Experimental Design Considerations and Limitations: CT Approach. The POSITScience BrainHQ treatment program was selected because it 1) provides specific training tasks directed at three essential cognitive domains tied to our aims and hypotheses (attention, working memory, executive control) that correspond with the neurocognitive and functional neuroimaging measures to be studied; (2) is shown to produce significant cognitive and functional improvements with good effect sizes in past RCTs (ACTIVE) with up to 10 year durability and transfer of training to measures of self-reported everyday functioning; 3) provides a “cognitive treatment engine²⁸²” which alone has a very high likelihood of yielding significant cognitive and functional

improvements, enabling us to test the augmenting effects of tDCS; and 4) is computerized, well standardized, and efficiently implemented.

Combined CT. We selected a combined CT approach rather than testing one specific training task: 1) This would optimize CT treatment effects for this primary intervention, providing a strong and reliable engine of change with which to examine effects of tDCS; 2) This approach enables us to affect several related cognitive functions that are strongly dependent on neural plasticity of the frontal cortex; and 3) This approach would maximize participants interest and motivation versus a single task that could become boring.

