Neuroimaging measures. We will focus on functional (fMRI) and cerebral metabolic (proton MRS) indices for two reasons: 1) These modalities are most linked to and likely sensitive to CT-associated neural plasticity and brain changes; and 2) Changes in these domains are likely to occur over the course of training compared to structural neuroimaging measures. We include active fMRI tasks related to the cognitive functions to be trained, as well as a passive resting state condition to examine the DMN. With respect to MRS, we use a single voxel method to achieve optimal sensitivity and will measure from one ROI (frontal). Along with Creatine (Cr), we will examine cerebral metabolites sensitive to neuronal loss and membrane disturbances (NAA, GLx), and pro-inflammatory processes (Ch, MI). We will also measure cerebral GABA concentrations using a state-of-the-art MRS approach that will reflect neural plasticity in ROIs. The MRS indices will be examined for Aims 2. We will also collect FLAIR imaging data to assess white matter hyperintensity load, as a possible predictor of treatment response (secondary aim)

6.3. Procedural sequence. The sequence and flow of the assessments to be conducted at baseline and each subsequent assessment is shown below. We describe participant recruitment and retention strategies in the Human Subjects section. We will inform potential participants about the study, and obtain their consent. We will then screen for inclusion/exclusion criteria and schedule them for baseline assessment visit #1 evaluation. All

[figure not shown]
following assessments are identical otherwise.

6.4 Cognitive Training. CT will involve up to 10 hours of training over 2-weeks (10 days). At the screening visit and post 2-week intervention participants will complete a 20-minute composite measure of the cognitive training tasks. *Training platform.* CT employs a PositScience BrainHQ suite via its researcher portal. These tasks are web-based and multi-platform (i.e., Windows, Mac). Participants will be randomly assigned to training on 4 tasks focusing on working memory or 4 tasks focusing on attention/speed of processing. Participants will be required to have a specific viewing distances. Study interventionists will provide daily performance summaries. The rationale and task demands for each component were described earlier (A.3.3). These CT are

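### Section 6.4 randomises participants between two training suites while 6.1 and 6.2 describe a one-factor, two-group trial: the sections must be reconciled, and suite, if it is real, declared and modelled

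*Combined protocol and SAP*

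**What the plan says.** All references are to the combined protocol and SAP.

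- **6.1 Experimental design:** "One factor with two levels [Factor 1 = stimulation type (active or sham) yields two cells". It then lists two conditions, active tDCS with CT and sham tDCS with CT, for 40 participants.
- **6.2 Randomization:** "We will use web-based permuted block randomization to randomly divide participants into the two groups". No ratio, block size, stratum or second allocation list is given.
- **6.4 Cognitive Training:** "Participants will be randomly assigned to training on 4 tasks focusing on working memory or 4 tasks focusing on attention/speed of processing". The same section has every participant complete a 20-minute composite of the training tasks at screening and after the intervention.
- **6.2.1, CT Approach:** BrainHQ was chosen because, among other reasons, it "provides specific training tasks directed at three essential cognitive domains tied to our aims and hypotheses", namely attention, working memory and executive control.
- **6.2.1, Combined CT:** "We selected a combined CT approach rather than testing one specific training task".
- **Game lists after 4.3.3:** four attention/speed games and four working-memory games, with no game in both. The working-memory list includes "Card Shark- N-back working memory task that varies on whether the current target matches stimuli presented 0-n steps before" and a second game of the same kind, Auditory Aces. The attention/speed list includes "Double Decision- requires visual search and selective attention to peripheral objects among distractors".
- **6.2.1, Neuroimaging measures:** "We include active fMRI tasks related to the cognitive functions to be trained". Section 6.6.1 gives the 2-Back and the UFOV task to everyone and says the 2-Back captures brain change caused by the study's n-back training.

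**The concern.** A second random assignment makes four cells, not two. Someone working from the protocol cannot tell whether a participant trains on one suite or on both, nor how suite is allocated.

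If 6.4 stands, three things follow.

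- The declared one-factor design is wrong.
- Some outcomes change meaning with suite. The 2-Back reflects n-back training only for people who received n-back games. H1.1 (amplified training effects) and H1.2 (near and far transfer) rest on the difference between trained and untrained material, yet neither mentions suite.
- A randomised factor left out of the model adds noise, including chance imbalance of suite between the stimulation arms. If outcomes are not classified by suite beforehand, the classification could be made after results are known.

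**Working it through.** **Step 1. Compare the texts.** The documents give no power calculation, so there is no figure to reproduce.

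| Item | 6.1 and 6.2 | 6.4 |
|---|---|---|
| Randomised factors | 1 (stimulation) | adds training suite |
| Cells | 2 | 2 x 2 = 4 |
| Size, if 1:1 throughout | 40/2 = 20 per arm | 40/4 = 10 per cell |

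6.2.1 does not settle the matter. Its three domains and combined approach fit one programme for everyone better, but four games within one suite could also be called combined. The two suites in 6.4 match the two four-game lists after 4.3.3, so 6.4 is not obviously a slip.

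**Step 2. Which outcomes depend on suite if 6.4 stands?**

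- *2-Back:* both n-back games are in the working-memory list only, so the 6.6.1 statement about n-back training holds for that suite alone.
- *UFOV fMRI task:* Double Decision, by its description the closest game, is in the attention/speed list only.
- *Posit composite (6.4):* given to all, so it may mix practised and unpractised games. Its content is not described.
- *Digit Span, Letter Number Sequencing, Symbol Digit Coding, NIH Toolbox:* not games in either list. The Abstract and 4.3.4 treat gains beyond the trained tasks as transfer, so these are transfer measures in both suites. Suite changes only how near the transfer is.

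**Step 3. Size.** Assumptions, none stated in the documents: 20 v 20, suites 20:20, two-sided 5%, 80% power, no dropout, within-suite SD of 1, and a suite difference s of 0.2, 0.5 or 1.0 SD.

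Detectable effect from the noncentral t, with SE = sqrt(2/20) = 0.316 SD:

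- no suite effect, no term (df 38): 0.909 SD
- suite term, suites balanced within arm (df 37): 0.910 SD
- suite left out: the SD is multiplied by sqrt(1 + 0.25 s^2) = 1.005, 1.031, 1.118, giving 0.914, 0.937 and 1.016 SD

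Power at a true effect of 0.909 SD (60,000 simulated trials):

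| Analysis | s = 0.2 | s = 0.5 | s = 1.0 |
|---|---|---|---|
| No stratification, no term | 79.6% | 77.6% | 70.6% |
| Term only | 78.9% | 78.9% | 78.9% |
| Stratified blocks and term | 79.8% | 79.8% | 79.8% |

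The gain from doing both is 0.2, 2.2 and 9.2 points. Stratification supplies 79.8 - 78.9 = 0.9 of that. The term alone loses 0.7 points at s = 0.2.

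Chance imbalance, with suite assigned independently of arm:

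- Hypergeometric (20 per suite, 20 per arm): 12 v 8 or worse has probability 0.343; 13 v 7 or worse, 0.113.
- Simple randomisation of suite: arms differ by at least 4 with probability 0.268, by at least 6 with probability 0.081.
- A 13 v 7 split moves the unadjusted arm difference by (13/20 - 7/20) s = 0.3 s = 0.06, 0.15 or 0.30 SD.

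This imbalance is already inside the first row of the power table and is not an additional loss.

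tDCS-by-suite interaction (df 36), SE = sqrt(sum of 1/n over the cells):

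- cells 10/10/10/10: SE 0.632, detectable at 1.82 SD
- cells 13/13/7/7: SE 0.663, detectable at 1.91 SD
- cells 15/15/5/5: SE 0.730, detectable at 2.10 SD

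**The case against.** The strongest reply is that the consequences are conditional and mostly small. 6.2.1 leans towards one programme for all, and on that reading only one sentence is wrong. The 6.3 flow figure and the attachments are not available here and may describe the allocation. The Abstract calls the trial a pilot, and the monitoring plan calls it exploratory. No suite effect is given anywhere, and a 1.0 SD gap is least plausible for tests that are transfer measures in both suites. Stratification adds about 1 point once suite is modelled, requires suite to be assigned before stimulation, and is of use only while randomisation is open; the documents give neither the order nor the enrolment status. The absence of an outcome model is general: the data management and analysis paragraph names only software. All of this stands, and it limits the claim about size. It does not remove the conflict between 6.4 and 6.1.

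A reader might also infer that every domain-specific test is trained in one suite and transfer in the other. The documents do not support that. The pencil-and-paper and Toolbox tests are games in neither suite, and labelling them as trained would put a new error into the plan. The Posit composite also gives the plan a measure of the trained tasks separate from the transfer battery.

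**Conclusion.** The contradiction holds, with high confidence: 6.4 cannot be squared with one factor, two cells and two groups. The 2x2 consequences carry moderate confidence, because they apply only if 6.4 is the intended design.

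Two stronger inferences should be resisted. The first is that the tDCS comparison is biased. It is not: with stimulation randomised, the pooled active-versus-sham contrast remains valid, and an unmodelled suite costs precision. The second is that pooling the suites dilutes the tDCS effect. Nothing in the documents shows this, and a suite term would not recover it.

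The main gain from correction is a correctly stated design and trained-versus-transfer results that can be interpreted. The power gain rests on the assumed suite difference and the other assumptions listed: nil at 0.2 SD, about 2 points at 0.5 SD, about 9 at 1.0 SD. The point should be fixed, but it does not undermine the primary contrast.

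**What to change.** Reconcile 6.1, 6.2, 6.2.1 and 6.4. The documents do not show which is intended, so the sponsor must say.

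If everyone receives both suites, correct the 6.4 sentence; nothing else on this point changes.

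If both suites stay:

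1. Declare suite in 6.1 and 6.2 as a second randomised factor, with its ratio and method.
2. Include suite as a term in the outcome models. If randomisation is still open and suite is assigned first, stratify the tDCS blocks by suite.
3. Before the data are examined, classify the 2-Back, the UFOV fMRI task and the components of the Posit composite as trained or untrained for each suite, and the other cognitive tests as near or far transfer for each suite. Limit the 6.6.1 statement on n-back training to the working-memory suite.
4. Report tDCS-by-suite as exploratory only.

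The cost is protocol wording, one degree of freedom (0.909 to 0.910 SD with suites balanced within arm) and, where still possible, one stratum in the existing web randomisation. No extra participants or visits are needed.
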